### **Evaluation of Left Ventricular Function**

All patients will undergo evaluation of LVEF, either by ECHO or MUGA at the following timepoints:

- Screening
- Cycle 2, Day 1  $\pm$ 1 week
- On Day 1 of Cycles 5, 8, and 11 (every 3 treatment cycles)  $\pm$ 2 weeks
- On Day 1 of Cycles 15, 19, and 23 (every 4 treatment cycles)  $\pm$ 2 weeks
- On Day 1 of Cycles 29, 35, 41, 47, etc. (every 6 treatment cycles)  $\pm$ 2 weeks
- End-of-study-treatment visit

For patients who cross over from placebo to cobimetinib treatment, the ECHO/MUGA schedule must begin again, with exams at the following timepoints:

- Within 28 days of, but not after the first day of cross over
- Start of second cycle after cross over, Day 1  $\pm$ 1 week
- On Day 1 of Cycles 5, 8, and 11 after cross over (every three treatment cycles)  $\pm$ 2 weeks
- On Day 1 of Cycles 15, 19, and 23 after cross over (every four treatment cycles)  $\pm$ 2 weeks
- On Day 1 of Cycles 29, 35, 41, 47 after cross over, etc. (every six treatment cycles)  $\pm$ 2 weeks
- End-of-study-treatment visit

See Section [4.5.1.11](#).

Guidelines for interruption/dose modification in the setting of decreased LVEF are provided in [Table 10](#).

#### **5.1.4.6 Hepatic Toxicity**

Grade 4 elevations of serum  $\gamma$  glutamyltransferase and other less severe liver function abnormalities have been reported in patients treated with vemurafenib and cobimetinib. These have generally been managed with interruption of treatment and dose reduction. All patients will undergo liver function testing (AST, ALT, total bilirubin, ALP, and  $\gamma$  glutamyltransferase) at periodic intervals while on study treatment (see [Appendix 1](#)). Guidelines for interruption/dose modification in the setting of liver function abnormality are provided in [Table 10](#).

### 5.1.5 Management of Specific Adverse Events

Dose levels for dose reductions are listed in [Table 9](#).

**Table 9 Dose Level Reductions**

Dose reduction	Vemurafenib	Cobimetinib
1 dose level	720 mg BID	40 mg QD
2 dose levels	480 mg BID	20 mg QD

BID=twice daily; QD=once daily.

Dose modifications, interruptions, and delays of vemurafenib and/or cobimetinib study treatment should be made on the basis of the guidelines provided in [Table 10](#). The dose modification guidelines are not intended to replace clinical judgment or dictate care of individual patients. Dose reduction of each study drug is independent of the other study drug. Dose re-escalation is not allowed.

#### 5.1.5.1 Rash Management

The appearance of rash must be differentiated as acneiform, non-acneiform or drug-induced photosensitive rash / sunburn.

Prior to starting study treatment, patients must be advised to:

- Avoid unnecessary or prolonged sun exposure while taking study treatment and for at least 5 days after discontinuation.
- Use broad-spectrum (UVA and UVB) sunscreen and lip balm (at least SPF > 30) to help protect against sunburn.
- Use thick, alcohol-free emollient cream (e.g. glycerine and cetomacrogol cream) on dry areas of the body.

For Grade 1 to 2 rash, the following supportive measures may be considered:

- For non-acneiform rash, mild strength topical steroid (e.g. hydrocortisone 1% cream).
- For acneiform rash, doxycycline 100 mg BID or minocycline 100 mg BID for 1–2 weeks.
- For pruritic lesions, the cool compresses and oral/topical antihistamine agents
- For photosensitive lesions / sunburn, use cool compresses and avoid further sun exposure.
- For desquamation, thick emollients and mild soap are recommended.

For Grade  $\geq 3$  rash, see [Table 10](#): management of specific toxicities and dose modification guidelines.

### 5.1.5.2 Diarrhea Management

Rule out other or concomitant causes, including medications (e.g., stool softeners, laxatives, antacids), infection by *Clostridium difficile*, malabsorption/lactose intolerance, fecal impaction, and dietary supplements high in fiber.

For Grade 1 to 2 diarrhea:

- Dietary modifications:
  - Stop all lactose-containing products and eat small meals.
  - The BRAT (banana, rice, apples, toast) diet may be helpful.
  - Encourage adequate hydration.
- Loperamide:
  - Suggested initial dose of 4 mg followed by 2 mg every 4 hours or after every unformed stool; up to a maximum of 16 mg/day.
  - Continue loperamide is suggested until diarrhea-free for 12 hours.
  - If Grade  $\leq 2$  diarrhea persists after 48 hours total treatment with loperamide, consider second-line agents (otretotide, budesonide, or tincture of opium).

For Grade  $\geq 3$  diarrhea, see [Table 10](#): Management of Specific Toxicities and Dose Modification Guidelines.

### 5.1.5.3 Management of Specific Toxicities and Dose Modification Guidelines

**Table 10 Management of Specific Toxicities and Dose Modification Guidelines**

Adverse Event	Action
A) Rash Grade $\geq 3$	
The appearance of rash must be characterized as acneiform or non-acneiform.
 
No change in vemurafenib and cobimetinib dosing will be implemented for Grade <math>\leq 2</math> rash; patients should receive maximal supportive care per institutional guidelines.
 
Acneiform rash
 
Hold cobimetinib dosing until Grade <math>\leq 2</math>.
 
Vemurafenib dosing may continue when cobimetinib is interrupted.
 
Reduce cobimetinib by 1 dose level. If after restarting at reduced dose, the patient experiences skin toxicity Grade <math>\geq 3</math>, further reduce cobimetinib by another dose level. Permanently discontinue cobimetinib if restarting after second dose reduction, the patient experiences skin toxicity Grade <math>\geq 3</math>.
 
Permanently discontinue cobimetinib if rash <math>\geq 3</math> persists for <math>> 28</math> days despite adequate supportive care.
 
Non-acneiform or maculo-papular rash
 
Delay vemurafenib dosing until Grade <math>\leq 2</math>.
 
Cobimetinib dosing may continue when vemurafenib is interrupted.
 
For Grade 3 rash, reduce vemurafenib by 1 dose level. If after restarting at reduced dose, the patient experiences skin toxicity Grade <math>\geq 3</math>, further reduce vemurafenib by 1 dose level.
 
Permanently discontinue vemurafenib if restarting after second dose reduction, the patient experiences recurrent skin toxicity Grade <math>\geq 3</math>.
 
For Grade 4 rash, reduce vemurafenib by 2 dose levels.
 
Permanently discontinue vemurafenib if after restarting at reduced dose, the patient experiences skin toxicity Grade <math>\geq 3</math>.

Table 10 Management of Specific Toxicities and Dose Modification Guidelines (cont.)							
Adverse Event	Action						
B) Photosensitivity Grade $\geq 3$	
a) Grade <math>\leq 2</math> photosensitivity should be managed with supportive care and treatment of both vemurafenib and cobimetinib may be continued.
 
If Grade 2 photosensitivity does not resolve to Grade <math>\leq 1</math> after 7 days or if photosensitivity worsens to Grade <math>\geq 3</math> despite best supportive care, then both vemurafenib and cobimetinib treatment must be interrupted until the photosensitivity resolves to a Grade <math>\leq 1</math>.
 
b) If resolution to Grade <math>\leq 1</math> occurs within 28 days, treatment may be re-initiated with vemurafenib dose reduced by 1 level and without change in cobimetinib dose.
 
If the photosensitivity does not resolve to Grade <math>\leq 1</math> by 28 days, then the therapy with vemurafenib and cobimetinib should be discontinued.
 
c) If the photosensitivity recurs to Grade <math>\geq 3</math> with vemurafenib and cobimetinib, re-initiation despite prophylactic measures and dose reduction of vemurafenib, then both agents should be held until the photosensitivity resolves to Grade <math>\leq 1</math> or less. The dose of vemurafenib should be reduced by another dose level.
 
d) If photosensitivity recurs a second time to Grade <math>\geq 3</math> despite prophylactic measures and the aforementioned 2 dose reductions of vemurafenib, vemurafenib should be discontinued. The patient may continue on study treatment with cobimetinib/placebo alone.
						

C) New skin lesion, suggestive of any cutaneous primary malignancy.
 
Any cutaneous primary malignancy is considered a Grade 3 event in this study.
	
a) Follow SCC Risk Management Plan detailed in protocol
 
b) Interrupt vemurafenib and cobimetinib for 48 hours before and after excisional biopsy. This period of interruption may be altered based upon experience in this study.
 
c) If lesion is diagnosed as cuSCC, treatment may be re-instituted with vemurafenib and cobimetinib at pre-event dose levels after the lesion is excised. If the lesion is not excised, vemurafenib treatment must be discontinued.
 
d) If the lesion is not an SCC, then treatment with vemurafenib and cobimetinib may be restarted at the most recent dose level.
						
D) Visual symptoms $\geq$ Grade 2	
NCI CTCAE v4.0 Eye Disorders – Other, specify:
 
  
 Grade	Description	
   
 1	Asymptomatic or mild symptoms; clinical or diagnostic observations only; intervention not indicated	
 
 2	Moderate; minimal, local or noninvasive intervention indicated; limiting age appropriate instrumental ADL	
  
	Grade	Description	1	Asymptomatic or mild symptoms; clinical or diagnostic observations only; intervention not indicated	2	Moderate; minimal, local or noninvasive intervention indicated; limiting age appropriate instrumental ADL
Grade	Description						
1	Asymptomatic or mild symptoms; clinical or diagnostic observations only; intervention not indicated						
2	Moderate; minimal, local or noninvasive intervention indicated; limiting age appropriate instrumental ADL						

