## **3. GO28141 STUDY DESIGN**

### **3.1 DESCRIPTION OF GO28141 STUDY DESIGN**

GO28141 is a multicenter, randomized, double-blind, placebo-controlled Phase III clinical study to evaluate the safety and efficacy of vemurafenib in combination with cobimetinib with vemurafenib alone, in previously untreated BRAFV600 mutation-positive patients with unresectable locally advanced or metastatic melanoma.

[figure not shown]
Approximately 500 previously untreated BRAFV600 mutation-positive patients with unresectable locally advanced or metastatic melanoma will be randomized in a 1:1 ratio to receive treatment with one of the following regimens:

- **Arm A (control arm):** vemurafenib 960 mg by mouth (PO) BID on Days 1–28 and placebo PO QD on Days 1–21 of each 28-day treatment cycle
- **Arm B (investigational arm):** vemurafenib 960 mg PO BID on Days 1–28 and cobimetinib 60 mg PO QD on Days 1–21 of each 28-day treatment cycle

The stratified, permuted-block randomization scheme will be used for treatment allocation based on the following stratification factors (Figure 4):

- Geographic region (North America, Europe, Australia/New Zealand/others)
- Metastatic classification (unresectable Stage IIIc, M1a, and M1b; or M1c)

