**Figure 5 Study GO28141 Dosing Scheme**

BID = twice daily; D = day; QD = once daily.

All patients will be closely monitored for safety and tolerability during all cycles of therapy, at the end-of-study treatment visit, and during the follow-up period. Patients will be assessed for adverse events every 2 weeks during the first 2 cycles, then prior to each subsequent cycle, and as necessary throughout the study.

Tumor response will be evaluated according to RECIST v1.1. Any evaluable and measurable disease must be documented at screening and re-assessed at each subsequent tumor evaluation. Response will be assessed by the investigator at 8-week intervals. At the investigator's discretion, CT/MRI scans may be repeated at any time if PD is suspected.

The NCI Common Terminology Criteria for Adverse Events (CTCAE) v4.0 will be used to characterize the toxicity profile of the study treatments on all patients. ECG monitoring for patients who receive vemurafenib will be conducted in accordance with the vemurafenib IB. Ongoing ECG monitoring is no longer required for patients who continue to receive only cobimetinib/placebo unless clinically indicated. Dermatologic assessment will be performed at the beginning of Cycle 2 ( $\pm 1$  week) and per local

standard of care thereafter. Ophthalmologic examinations and left ventricular function evaluation (echocardiogram or MUGA) are evaluated throughout the study.

Treatment will continue until disease progression, death, unacceptable toxicity, or withdrawal of consent, whichever occurs earliest. Patients on the vemurafenib and placebo treatment arm will be eligible to cross over to the vemurafenib and cobimetinib treatment arm prior to disease progression so long as the patient has not discontinued vemurafenib treatment should the investigator feel that the addition of cobimetinib may benefit the patient and the patient provides informed consent and continues to be followed for survival. Patients who have previously discontinued vemurafenib and who are receiving only placebo may not cross over and should discontinue all study treatment.

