#### **4.2 METHOD OF TREATMENT ASSIGNMENT, BLINDING, AND UNBLINDING**

After written informed consent has been obtained and eligibility has been established, each patient will be assigned an identification number and be randomized to 1 of the 2 treatment arms through use of an IxRS.

Randomization will be stratified by metastatic stage (unresectable Stage IIIc, M1a, and M1b; M1c) and region (North America, Europe, Australia/New Zealand/others). A stratified, permuted, block randomization scheme will be used to obtain approximately a 1:1 ratio between the 2 treatment groups. There is no pre-specified gender or ethnicity distribution in this study. It is expected that enrollment into this study will be representative of the gender and ethnicity distribution found in patients with unresectable or metastatic melanoma in the participating countries.

The investigator, patient, and Sponsor will be blinded to treatment assignment until completion of the final efficacy analysis of OS.

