#### **Prior to unblinding at the final overall survival efficacy analysis:**

Treatment codes should not be broken except in emergency situations. In such cases, the IxRS system will be used to allow disclosure of an individual patient's treatment assignment to the treating investigator. If the investigator wishes to know the identity of the study drug for any other reason, he or she should contact the Medical Monitor directly. The investigator should document and provide an explanation for any

premature unblinding (e.g., accidental unblinding, unblinding due to a serious adverse event).

Per health authority reporting requirements, the treatment code will be available through IxRS to the Roche Drug Safety Group for all unexpected serious adverse events that are considered by the Investigator to be related to study drug (see Section 5.7).

The investigator may request unblinding of a patient's treatment assignment only when knowledge of the investigational product is essential for the safety of the patient. In such cases, the IxRS system will be used to allow disclosure of an individual patient's treatment assignment to the treating investigator. Any site requests for unblinding, for any reason apart from emergency situations, require consultation with the Roche Medical Monitor.

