#### **4.3.2.1 Cobimetinib/Placebo**

Cobimetinib or placebo should be taken once daily at approximately the same time each day with the morning vemurafenib dose, and no later than 4 hours after the scheduled time.

Cobimetinib or placebo can be taken with or without a meal. Cobimetinib or placebo tablets should never be chewed, cut, or crushed.

Upon completion of the final OS analysis, patients in the placebo arm who are unblinded and choose not to cross over to cobimetinib will no longer need to receive placebo and will continue to receive vemurafenib only, unless they had previously discontinued vemurafenib, in which case they will discontinue all study treatment.

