##### **4.4.2 Prohibited Therapy**

Use of the following therapies is prohibited during the study and for at least 14 days prior to initiation of study treatment, unless otherwise specified below:

- Any prior or concomitant therapy intended for the treatment of advanced melanoma, either approved by health authorities or experimental, including chemotherapy, radiation therapy, immunotherapy, hormonal therapy, biologic therapy, or investigational agents is prohibited. Patients who received prior adjuvant immunotherapy are allowed on the study.

- Palliative radiotherapy or major surgery within 14 days prior to first dose of study treatment is prohibited.

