H) QTcF interval prolongation on ECG Grade ≥ 3	
a) Rule out other risk factors for arrhythmia (e.g., myocardial ischemia); check for electrolyte disturbances (particularly potassium and magnesium levels) in all cases.
 
b) Evaluate concomitant medications to determine if there is co-administration of drugs that prolongs QTc interval in all cases (e.g., 5-HT3 receptor antagonist anti-emetics; see Appendix 9).
 
c) Interrupt dosing of vemurafenib ECG monitoring should be performed until QTc interval decreases below 500 ms. Electrolytes abnormalities should be corrected in all cases. Continue dosing with cobimetinib at the current dose if otherwise tolerated.
 
d) Plan to seek a cardiologist consultation or advice.
 
e) If QTc interval does not improve within 28 days after interruption of vemurafenib dosing, permanently discontinue vemurafenib; continue dosing with cobimetinib at the current dose.
 
f) If QTc improves within 28 days, restart dosing of vemurafenib at 1 reduced dose level.
 
g) Repeat 12-lead ECG monitoring at 2 weeks and 4 weeks of restarting vemurafenib at the lower dose. Additional ECG monitoring will be performed at Day 15 of each subsequent Cycle for 3 cycles, and every 3 months thereafter.
 
h) If second increase in QTc interval to > 500 ms occurs at the lower dose of vemurafenib, follow guidelines above, and reduce dose of vemurafenib by an additional dose level.
 
i) Permanently discontinue vemurafenib if after correction of associated risk factors and dose reductions, the QTc increase meets values of both > 500 ms and > 60 ms change from pre-treatment values.

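### Table 10 lets a patient taken off vemurafenib stay on cobimetinib/placebo alone, while Section 3.1 and the synopsis tell placebo-only patients to stop all study treatment

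*Protocol*

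**What the plan says.** Section 3.1 defines the control arm as "vemurafenib 960 mg by mouth (PO) BID on Days 1–28 and placebo PO QD on Days 1–21 of each 28-day treatment cycle". Removing vemurafenib therefore leaves placebo.

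Two rows of Table 10 (Section 5.1.5.3) expressly continue the second drug after vemurafenib is stopped for good:

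- Row B(d), recurrent photosensitivity: "The patient may continue on study treatment with cobimetinib/placebo alone".
- Row H(e), QTc not improving within 28 days of interruption: "permanently discontinue vemurafenib; continue dosing with cobimetinib at the current dose".

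The cross-over paragraph of Section 3.1, repeated in the synopsis, says: "Patients who have previously discontinued vemurafenib and who are receiving only placebo may not cross over and should discontinue all study treatment". Section 4.3.2.1 has a matching rule for placebo patients who are unblinded and do not cross over, but opens it with completion of the final OS analysis: they go on with vemurafenib only, "unless they had previously discontinued vemurafenib, in which case they will discontinue all study treatment".

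Other text treats continuing without vemurafenib as an ordinary state. Section 3.1 itself and Section 4.5.1.11 waive routine ECGs for patients who are off vemurafenib and still taking cobimetinib or placebo.

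On blinding, Section 4.2 states: "The investigator, patient, and Sponsor will be blinded to treatment assignment until completion of the final efficacy analysis of OS". Before that point, "Treatment codes should not be broken except in emergency situations", although the same section sends requests made for other reasons to the Medical Monitor.

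**The concern.** For an Arm A patient whose vemurafenib has been permanently stopped, Table 10 allows study treatment to go on and Section 3.1 says it should end. What is at stake is whether a patient with unresectable or metastatic melanoma stays on placebo alone. While such a patient counts as on study treatment, Section 4.4.2 prohibits other treatment for the disease ("Any prior or concomitant therapy intended for the treatment of advanced melanoma"), and Section 3.2 foresees subsequent anti-cancer treatment only after study treatment has ended.

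The Section 3.1 rule also turns on knowing that the tablet is placebo, which a blinded site does not know. Table 10, the text a site would consult when managing the toxicity, does not refer to that rule.

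**Working it through.** The plan gives no figure for this point, so the check is a comparison of the passages by patient state.

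| Patient after permanent vemurafenib discontinuation | Table 10 | Section 3.1 and synopsis | Section 4.3.2.1 | Result |
|---|---|---|---|---|
| Arm A, still blinded, row B(d) | May continue (placebo only) | Stop all study treatment | Not yet in force | Conflict |
| Arm A, still blinded, row H(e) | Continue; the blinded counterpart of cobimetinib is placebo | Stop all study treatment | Not yet in force | Conflict |
| Arm A, unblinded, not crossed over, already off vemurafenib | B(d) wording still permits continuing | Stop | Stop | B(d) not updated; the other two agree |
| Arm B, or Arm A after cross-over | Continue cobimetinib | Does not apply | Does not apply | No conflict |

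An unblinded Arm A patient still on vemurafenib who declines cross-over no longer receives placebo (Section 4.2). If vemurafenib then stops, B(d) has nothing left to continue.

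The live conflict is therefore in the first two lines. Neither Section 3.1 nor Table 10 says which period it governs. The mandatory stopping reasons in Section 4.6.1.1 do not settle it either: discontinuing vemurafenib while on placebo is not among them.

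**Scale.** The protocol does not report how many patients permanently stopped vemurafenib alone. Two figures help.

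1. Row B(d). Section 5.1.2.1 reports Grade 3 or higher photosensitivity as 4% with cobimetinib and 0% in the control arm. Taking n = 248 (Section 1.4.4) and assuming that 0% means no patients, the one-sided 95% upper bound is 1 − 0.05^(1/248) ≈ 1.2%. Rounding would also allow one patient, since 1/248 = 0.4%. Row B(d) further requires a second Grade 3 or higher recurrence after two vemurafenib reductions, so it is likely to have reached few or no control patients.
2. Row H(e). Section 1.2.5.4 reports QTc above 500 ms in 2 of 132 patients (1.5%) on single-agent vemurafenib in Phase II. If that proportion held here (an assumption), 248 × 2/132 ≈ 3.8, so about 4 control patients would enter row H. Only those with no improvement within 28 days would reach (e).

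**The case against.** The strongest reply is that the rules cover different periods. The Section 3.1 sentence sits in the cross-over paragraph and speaks of patients known to be on placebo, which presupposes unblinding. Section 3.3.3 places cross-over after the key assessments, Appendix 1 footnote 2 ties it to unblinding under version 6, and Section 4.3.2.1 restates the stop rule for unblinded patients. Table 10 uses the language of the blinded period. This reading is plausible and may be what was intended, but neither Section 3.1 nor Table 10 states it. The instruction to discontinue all study treatment is also a separate part of the sentence from the bar on cross-over.

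Several limits on the point do stand:

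- Row B(d) is permissive, Section 5.1.5 says the guidelines do not replace clinical judgment, and Section 4.6.1 lets the patient or investigator stop study drug at any time. No one is locked in.
- A reader might infer that the arm can be learned only in an emergency. Section 4.2 gives another route through the Medical Monitor, though it confines requests to what is essential for the patient's safety.
- A reader might count rows A, C(c) and H(i) as well. These can stop vemurafenib permanently but do not say that cobimetinib/placebo then continues. Row A allows that only while vemurafenib is interrupted.
- Under version 8 the final OS analysis is done (data cutoff 28 August 2015, Section 1.4.4). Section 4.2 releases assignments once the local IRB/EC approves, so a blinded control patient could remain only where that approval is pending.

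**Conclusion.** The contradiction is real and stands in current text. For a blinded Arm A patient permanently off vemurafenib under row B(d) or H(e), Table 10 and Section 3.1 point in opposite directions, and the site cannot apply Section 3.1 unaided. It is narrow: few patients are likely to be affected, and the case is largely historical at version 8. It still deserves correction because it bears directly on whether a patient remains on placebo alone.

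A reader might go further and infer that placebo-only time in the control arm biased PFS in favour of the combination. The document does not support that. It gives neither a rate of permanent vemurafenib-only discontinuation nor outcomes afterwards, so any shift in the hazard ratio would rest on assumed inputs. The Grade 3 or higher rash and liver-test frequencies in Section 5.1.2 give no permanent discontinuation rate. For the same reason the point does not call for a PFS analysis censored at vemurafenib discontinuation. Toxicity-driven censoring may be informative, it departs from the intent-to-treat analysis of Section 6.4, and the primary PFS analysis has already been reported (cutoff 9 May 2014).

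The conclusion rests on the wording of the passages. The scale rests on the assumptions stated with the figures.

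**What to change.** Reconcile the synopsis, Section 3.1, Section 4.3.2.1, Section 4.5.1.11 and Table 10 rows B(d) and H(e) into one rule for a patient whose vemurafenib is permanently stopped. State whether it covers the blinded period, the unblinded period or both. If it depends on the arm, refer to the existing Medical Monitor route in Section 4.2, so that a blinded site knows how to proceed. Add a cross-reference from Table 10 to the rule.

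Which rule applies is for the clinical team to decide; this review takes no position on it.

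The cost is wording in two table rows and a few sections, with no change to the analyses or data collection. If the chosen rule depends on the arm, a few remaining blinded patients might be unblinded earlier than otherwise.
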